7. SCHEDULE OF EVENTS AND STUDY PARAMETERS

7.1. Schedule of Events

The proposed types and timing of data to be recorded are described in Table 4 below. Please see Section 7.2 for cross-referenced explanations of the study procedures described in the tables.

Table 4. Schedule of Events

		Baseline	Ataluren Treatment					
Period	Screening*	a a	Audich Heddich					Post-Treatment
Study Week (±7 days)	-4 to -1	Week 1	Every 60 Weeks	Every 12 Weeks	Every 24 Weeks	Every 48 Weeks	End of Tx Week 240	6 Week Post D/C
Informed Consent {7.2.2}	x							
Clinical/medication history (7.2.3)	x							
Hepatitis screen {7.2.4}	x							
Vital signs {7.2.5}	x	x		x			x	X
Brooke UE Functional Rating Scale {7.2.6}	x							
Height/Ulna length/Arm Span {7.2.7}	x				x		x	
Physical examination (7.2.8)	x					x	x	
Weight {7.2.9}	x	x		x			x	×
Hematology {7.2.10}	x	x		x			x	x
Biochemistry {7.2.11}	x	x		x			x	x
ACTH and cortisol {7.2.12}	x	x		x			x	x
Renin and aldosterone {7.2.12}	x				As Indicated	I		
Urinalysis (7.2.13)	X	X		X			X	X
12-lead ECG {7.2.14}	x				As Indicated	l		
Echocardiogram {7.2.15}	x		X			X		χ ^b
6-minute walk test {7.2.16}	x				x		x	
Timed Function Tests {7.2.17}	x					X	x	
North Star Ambulatory Assessment {7.2.18}	x					X	x	
Egen Klassifikation Scale {7.2.19}	x					X	x	
Spirometry (7.2.20)	X				X		X	
Disease status survey {7.2.21}	x	X		x			X	
Drug administration {7.2.22}		x		x				
Drug compliance {7.2.23}				x			X	
Adverse events {7.2.24}		x		x			X	X
Concomitant medications {7.2.25}	x	x		x			X	X

Ataluren may be initiated as soon as the investigator confirms patient eligibility. Baseline procedures (excluding drug administration) do not need to be performed if Screening procedures have been performed within 7 days of anticipated initiation of ataluren treatment.

Abbreviations: ACTH = adrenocorticotropic hormone, D/C = discontinuation, ECG = electrocardiogram, Tx = treatment, UE = upper

b Only applies to patients who discontinue the study after 240 weeks of treatment.

extremity

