7.2.1.2. Treatment Visits during Study

Each subject will subsequently return to the clinical research facility during Week 12 (Visit 3), Week 24 (Visit 4), Week 36 (Visit 5), Week 48 (Visit 6), Week 60 (Visit 7), Week 72 (Visit 8), Week 84 (Visit 9), Week 96 (Visit 10), Week 108 (Visit 11), Week 120 (Visit 12), Week 132 (Visit 13), Week 144 (Visit 14), Week 156 (Visit 15), Week 168 (Visit 16), Week 180 (Visit 17), Week 192 (Visit 18), Week 204 (Visit 19), Week 216 (Visit 20), Week 228 (Visit 21) and Week 240 (Visit 22).

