7.2.10. Hematology Laboratory Assessment

Hematology laboratory assessments will include white blood cell count with differential, hemoglobin, hematocrit, mean corpuscular volume, mean corpuscular hemoglobin, mean corpuscular hemoglobin concentration, total red cell count with morphology, and platelet count. These parameters will be measured at Screening (Visit 1), Week 1 (Visit 2), Week 12 (Visit 3), Week 24 (Visit 4), Week 36 (Visit 5), Week 48 (Visit 6), Week 60 (Visit 7), Week 72 (Visit 8), Week 84 (Visit 9), Week 96 (Visit 10), Week 108 (Visit 11), Week 120 (Visit 12), Week 132 (Visit 13), Week 144 (Visit 14), Week 156 (Visit 15), Week 168 (Visit 16), Week 180 (Visit 17), Week 192 (Visit 18), Week 204 (Visit 19), Week 216 (Visit 20), Week 228 (Visit 21), Week 240 (Visit 22 End-of-Treatment/Premature Discontinuation) and at the Post-Treatment Visit (6 weeks post discontinuation of ataluren). Hematology parameters will be analyzed by the central laboratory. The Covance Central Laboratory Manual should be consulted for collection, processing, and shipping details.

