5 STATISTICAL ANALYSIS

5.1 General Statistical Considerations

Summary tables for continuous variables will contain the following statistics: n, mean, standard deviation, standard error, 95% confidence intervals (CIs) on the mean, median, minimum, and maximum. Summary tables for categorical variables will include N, n, and percentages. In by-visit summaries, the analysis visits will be derived via visit mapping windows.

By-patient listings will be created for each CRF module. The data will be listed by center/subject ID and visit.

In addition, all analyses will be performed by corticosteroid use (yes or no before or during the study), by ambulatory status (ambulatory or non-ambulatory) at baseline, and overall, unless specified otherwise.

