5.7.2 Laboratory Tests

Hematological, serum biochemistry, adrenal laboratories, and urine data and their changes (only for continuous laboratory parameters) from baseline will be summarized by visit.

Shift tables for hematology and biochemistry data will also be presented showing change in CTCAE severity grade from baseline to each visit. For parameters for which a CTCAE scale does not exist, shift tables will be presented showing change in results from baseline (normal, low and high [or abnormal]) to each visit (normal, low and high [or abnormal]).

Summary of abnormalities in laboratory variables pre-defined for safety monitoring will be done per the following Table 2.

Table 2: Safety Monitoring Parameters and Actions to be Taken

Organ System and Laboratory Parameter	Stop Study Drug Immediately, Confirm Abnormal Value, and Then Start Work-Up	Stop Study Drug After Confirming ^a Abnormal Value, and Then Start Work-Up	Continue Study Drug, Confirm Abnormal Value, and then Start Work-Up ^a
Hepatic			
Serum total bilirubin	\geq Grade 3 ($\geq 3.0 \times$ ULN)	Grade 2 (1.5 – 3.0 x ULN)	---
Serum GGT	\geq Grade 3 ($\geq 5.0 \times$ ULN)	Grade 2 ($>2.5 - 5.0 \times$ ULN)	---
Serum ALT			\uparrow of >150 U/L with stable or \downarrow CK
Adrenal			
Plasma ACTH	---	$>$ ULN (and plasma cortisol $<$ LLN)	$>$ ULN (and cortisol WNL)
Renal			
Serum cystatin C	>2.00 mg/L	$>1.33 - 2.00$ mg/L	---
Serum creatinine	\geq Grade 2 ($\geq 1.5 \times$ ULN for age)	Grade 1 ($>$ ULN – $1.5 \times$ ULN for age)	---
Serum BUN	$\geq 3.0 \times$ ULN	$\geq 1.5 - 3.0 \times$ ULN	---
Urine protein: urine creatinine (spot)	---	>0.40 mg:mg	---
Urine protein: urine osmolality (spot)	---	>0.30 mg/L:mOsm/kg	---
Urine blood (by dipstick)	4+ (Large)	3+ (Moderate)	2+ (Small)

Organ System and Laboratory Parameter	Stop Study Drug Immediately, Confirm Abnormal Value, and Then Start Work-Up	Stop Study Drug After Confirming ^a Abnormal Value, and Then Start Work-Up	Continue Study Drug, Confirm Abnormal Value, and then Start Work-Up ^a
Serum electrolytes	Grade 3-4	Grade 2	Grade 1
Serum Na ⁺ , high	>155 mmol/L	>150 – 155 mmol/L	---
Serum Na ⁺ , low	<130 mmol/L	---	---
Serum K ⁺ , high	>6.0 mmol/L	>5.5 – 6.0 mmol/L	---
Serum K ⁺ , low	<3.0 mmol/L	---	---
Serum Mg ²⁺ , high	>1.23 mmol/L	---	---
Serum Mg ²⁺ , low	<0.4 mmol/L	<0.5 – 0.4 mmol/L	---
Total serum Ca ²⁺ , high	>3.1 mmol/L	>2.9 – 3.1 mmol/L	---
Total serum Ca ²⁺ , low	<1.75 mmol/L	<2.0 – 1.75 mmol/L	---

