6 DATA HANDLING

6.1 Analysis Visits based on Visit Windows

Since some subjects had early terminations or unscheduled visits in during, the derived analysis visits will be generated by visit window defined as follows.

The derived visits will be generated by visit window defined as follows.

Let ADY=assessment date –first dose date +1.

```
IF .<= ADY <=1 THEN AVISIT= BASELINE AND AVISITN=1;
IF 42<= ADY <=126 THEN AVISIT=WEEK 12 AND AVISITN=2;
IF 126<ADY <=210 THEN AVISIT=WEEK 24 AND AVISITN=3;
IF 210<ADY <=294 THEN AVISIT=WEEK 36 AND AVISITN=4;
IF 294<ADY <=378 THEN AVISIT=WEEK 48 AND AVISITN=5;
IF 378<ADY <=462 THEN AVISIT=WEEK 60 AND AVISITN=6;
IF 462<ADY <=546 THEN AVISIT=WEEK 72 AND AVISITN=7;
IF 546<ADY <=630 THEN AVISIT=WEEK 84 AND AVISITN=8;
IF 630<ADY <=714 THEN AVISIT=WEEK 96 AND AVISITN=9;
IF 714<ADY <=798 THEN AVISIT=WEEK 108 AND AVISITN=10;
IF 798<ADY <=882 THEN AVISIT=WEEK 120 AND AVISITN=11;
IF 882<ADY <=966 THEN AVISIT=WEEK 132 AND AVISITN=12;
IF 966<ADY <=1050 THEN AVISIT=WEEK 144 AND AVISITN=13;
IF 1050<ADY <=1134 THEN AVISIT=WEEK 156 AND AVISITN=14;
IF 1134<ADY <=1218 THEN AVISIT=WEEK 168 AND AVISITN=15;
IF 1218<ADY <=1302 THEN AVISIT=WEEK 180 AND AVISITN=16;
IF 1302<ADY <=1386 THEN AVISIT=WEEK 192 AND AVISITN=17;
IF 1470<ADY <=1554 THEN AVISIT=WEEK 216 AND AVISITN=19;
IF 1554<ADY <=1638 THEN AVISIT=WEEK 228 AND AVISITN=20;
IF 1638<ADY <=1722 THEN AVISIT=WEEK 240 AND AVISITN=21
IF 1722<ADY <=1806 THEN AVISIT=WEEK 252 AND AVISITN=22
IF 1806<ADY <=1890 THEN AVISIT=WEEK 264 AND AVISITN=23
IF 1890<ADY <=1974 THEN AVISIT=WEEK 276 AND AVISITN=24
IF 1974<ADY <=2058 THEN AVISIT=WEEK 288 AND AVISITN=25
IF 2058<ADY <=2142 THEN AVISIT=WEEK 300 AND AVISITN=26
```

IF 2142<ADY <=2226 THEN AVISIT=WEEK 312 AND AVISITN=27

IF 2226<ADY <=2310 THEN AVISIT=WEEK 324 AND AVISITN=28

IF 2310<ADY <=2394 THEN AVISIT=WEEK 336 AND AVISITN=29.

If there are more than 1 valid assessment within one visit window, the last one will be chosen as the analysis value.

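### SAP 6.1 has no analysis window for Week 204 (days 1387 to 1470), so a scheduled safety visit drops out of every by-visit output

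*SAP*

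**What the plan says.** SAP 5.1 sets the general rule: "In by-visit summaries, the analysis visits will be derived via visit mapping windows". SAP 6.1 then defines study day ("Let ADY=assessment date –first dose date +1") and lists one mapping line per 12-weekly visit from Week 12 (AVISITN 2) to Week 336 (AVISITN 29). Two consecutive lines matter here:

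- "IF 1302<ADY <=1386 THEN AVISIT=WEEK 192 AND AVISITN=17"
- "IF 1470<ADY <=1554 THEN AVISIT=WEEK 216 AND AVISITN=19"

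The protocol, section 7.2.1.2, lists the late treatment visits as "Week 204 (Visit 19), Week 216 (Visit 20), Week 228 (Visit 21) and Week 240 (Visit 22"), so Week 204 is a scheduled visit. Protocol sections 7.2.5, 7.2.9 to 7.2.13 and 7.2.21 place vital signs, weight, haematology, biochemistry, ACTH and cortisol, urinalysis and the disease status survey at it.

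SAP 5.7.2 builds the laboratory outputs by visit: "Hematological, serum biochemistry, adrenal laboratories, and urine data and their changes (only for continuous laboratory parameters) from baseline will be summarized by visit". It also calls for shift tables from baseline to each visit for haematology and biochemistry. Vital signs (SAP 5.7.3) and the prospective survey (SAP 5.8.6) are likewise summarised by visit.

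**The concern.** The windows are meant to run on from one another, and the list breaks at exactly one scheduled visit. Nothing else in the SAP picks up the unassigned days. There is no nearest-visit rule and no return to the visit label on the case report form. SAP section 1 gives the SAP precedence over the protocol where they conflict, so the protocol's visit list does not repair the gap. SAP section 7, which records changes from the protocol, mentions no removal of Week 204.

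The primary endpoint is long-term safety and includes laboratory abnormalities. A late on-treatment visit, nearly four years in, is where by-visit laboratory trends carry information that the earlier, shorter studies could not supply.

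There is also an efficacy consequence. Under protocol section 7.2.1.3, a patient who stops early and was last seen more than 3 weeks before has the Week 240 procedures done at a Premature Discontinuation Visit. Patients moving to commercial drug have an End-of-Treatment Visit. If such a visit falls on days 1387 to 1470, its 6MWT, timed function, NSAA, EK or spirometry values have no analysis visit. For 6MWT and the timed function tests they also cannot enter the MMRM, where visit is a categorical factor (SAP 5.8.1 and 5.8.2). These are the last values of boys leaving the study, so their loss need not be neutral.

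**Working it through.** **Inputs**

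- Study day: assessment date minus first dose date plus 1 (SAP 6.1).
- Window limits and AVISITN values as printed in SAP 6.1.
- Scheduled visits: every 12 weeks, Weeks 12 to 240 (protocol 7.2.1.2). SAP section 1 extends the maximum to Week 336 for Canadian sites.
- Visit tolerance: ±7 days (protocol Table 4).

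**Step 1: the list's own pattern.** For visit week w, the printed lines follow: first day = 7w − 41, last day = 7w + 42, AVISITN = w/12 + 1.

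| Week | 7w | First day | Last day | AVISITN | Printed in SAP 6.1? |
|---|---|---|---|---|---|
| 192 | 1344 | 1303 | 1386 | 17 | yes |
| 204 | 1428 | 1387 | 1470 | 18 | **no** |
| 216 | 1512 | 1471 | 1554 | 19 | yes |

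Every printed line fits the pattern except Week 12, which starts at day 42 rather than 43.

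**Step 2: count the lines.** Weeks 12 to 336 in steps of 12 give 336/12 = 28 visits, which need AVISITN 2 to 29. The SAP prints 27 lines, and 18 is the only number skipped.

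**Step 3: map every day.** Applying the printed rules to each study day up to 2394 leaves two unassigned runs:

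- Days 2 to 41 (40 days), before the Week 12 window. No routine visit after the first dose is scheduled there, and this run is a separate matter.
- Days 1387 to 1470 (84 days).

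**Step 4: place the Week 204 visit.** Taking nominal day 7w = 1428, the tolerance gives days 1421 to 1435. Taking 7w + 1 = 1429, because the first dose is day 1, it gives days 1422 to 1436. Over both conventions these are 16 days, and 0 of the 16 map to any analysis visit. Week 204 is the only 12-weekly visit from Week 12 to Week 336 for which this happens. Measured from day 1428, a visit would have to be 1428 − 1386 = 42 days early or 1471 − 1428 = 43 days late to be mapped at all, and it would then count as Week 192 or Week 216.

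**Step 5: size.** Weeks 12 to 240 contain 240/12 = 20 post-baseline visits, so 1/20 = 5% of the 12-weekly schedule under protocol Version 5.0 is lost. Against all 28 visits to Week 336 the share is 1/28 = 3.6%.

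**Step 6: test the repair.** With days 1387 to 1470 assigned to Week 204, no day from 42 to 2394 is unmapped, and all of days 1421 to 1436 map to Week 204.

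**The case against.** The strongest reply accepts the gap and disputes its weight.

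- **Much of the safety analysis does not use the windows.** Treatment-emergent and serious adverse event tables, exposure-adjusted rates and by-patient listings are unaffected. The summary of pre-defined laboratory abnormalities (SAP Table 2) and the count of patients meeting hypertension criteria are not stated to be by visit, so a threshold breach at Week 204 need not be lost. This stands, and it limits the finding to window-based outputs.
- **Efficacy exposure is small.** 6MWT and spirometry are scheduled every 24 weeks and the timed function tests, NSAA and EK every 48, so none is due at Week 204. The Kaplan-Meier analyses of loss of ambulation and FVC below 1 litre use ages at events or assessments, not windows. This also stands. The number of discontinuation visits on days 1387 to 1470 cannot be found from the documents, and some exits, such as sponsor termination or transfer to commercial drug, may not be informative.
- **5% is a share of visits, not of data.** Correct. Attrition by Week 204 is not given, so the share of samples may be lower.
- **The slip is obvious.** The jump in AVISITN from 17 to 19 shows that a line was intended, and a programmer would probably notice. A line lost in converting the PDF to text cannot be wholly excluded either. Both are reasons to check the source document and the program. Neither makes the printed rule executable: followed literally it drops the visit, and anything else is an undocumented choice.
- **No hypothesis test depends on it.** The study is open-label and single-arm, and its sample size rests on no formal hypothesis. True, but by-visit laboratory summaries and shift tables are planned analyses of the primary endpoint.

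**Conclusion.** The concern holds. As written, SAP 6.1 gives no analysis visit to any assessment on days 1387 to 1470, and every on-time Week 204 visit falls there. For that visit the loss is complete in the by-visit laboratory, vital-sign, weight and survey summaries and in the haematology and biochemistry shift tables. It amounts to one of 20 scheduled post-baseline visits to Week 240. Discontinuation or unscheduled efficacy tests on those days drop out of the by-visit tables and, for 6MWT and timed function tests, out of the MMRM; how many cannot be determined from the documents. Adverse event incidence, exposure-adjusted rates and listings are untouched.

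The conclusion rests on two assumptions: that the SAP text matches the approved document at this point, and that the derivation program follows the printed rules. This is a rule that is wrong as printed, not a missing detail, and it should be corrected before the analysis is run.

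**What to change.** Insert one line between the Week 192 and Week 216 lines of SAP 6.1:

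`IF 1386<ADY <=1470 THEN AVISIT=WEEK 204 AND AVISITN=18;`

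First check the original SAP and the derivation program, and confirm that all three agree after the change. If the by-visit outputs have already been produced, rerun them along with the shift tables and the MMRM.

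The line follows the list's own pattern, alters no other window and needs no new data. The cost is one line in the SAP and one in the program. Days 2 to 41 stay unmapped, which affects no routine visit.

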6.2 Baseline

In general, Baseline is defined as the last non-missing valid assessment prior to or on the date of the first dose.

6.3 Absolute and Relative Change from Baseline

The absolute change from baseline at each post-baseline visit is calculated as (post-baseline value – Baseline), while the relative change (%) from baseline at each post-baseline visit is calculated as (post-baseline value – Baseline)/Baseline×100.

6.4 Missing Dates of AE and Prior and Concomitant Medications

6.4.1 Missing Date Information for Adverse Events

The following imputation rules only apply to cases in which the start date is incomplete (ie, partially missing) for adverse events.

Missing day and month

- If the year is same as the year of the date of the first dose of double-blind study drug, then the day and month of the date of the first dose of double-blind study drug will be assigned to the missing fields.
- If the year is prior to the year of the date of the first dose double-blind study drug, then December 31 will be assigned to the missing fields.
- If the year is after the year of the date of the first dose double-blind study drug, then January 1 will be assigned to the missing fields.

Missing month only

- The day will be treated as missing and both month and day will be replaced according to the above procedure.

Missing day only

- If the month and year are same as the year and month of the date of the first dose double-blind study drug, then the date of the first dose double-blind study drug will be assigned to the missing day.
- If either the year is before the year of the date of the first dose of double-blind study drug or if both years are the same but the month is before the month of the date of the first dose of double-blind study drug, then the last day of the month will be assigned to the missing day.

- If either the year is after the year of the date of the first dose of double-blind study drug or if both years are the same but the month is after the month of the date of the first dose of double-blind study drug, then the first day of the month will be assigned to the missing day.

If the stop date is complete and the imputed start date as above is after the stop date, the start date will be imputed by the stop date.

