5.8.2 Timed Function Tests

Timed function test data (ie, time to stand from supine and time to run/walk 10 meters) and change from baseline to each post baseline visit will be summarized descriptively by visit for ambulatory subjects with non-missing baseline timed function tests assessments. Similarly the time to stand from supine and time to run/walk 10 meters will also be summarized for each actual age.

Timed function test (TFT) data imputation rules as the following will be used in the summary.

- If time to run/walk 10 meters > 30 sec, then set to 30 sec.
- If time to stand from supine > 30 sec, then set to 30 sec.

Similar to 6MWT, the time to stand from supine and time to run/walk 10 meters of will also be analyzed by means of a mixed model repeated measures (MMRM) where baseline is baseline time taken to stand from supine and time taken to run/walk 10 meters, respectively.

The Kaplan-Meier method will be applied to the analysis of age at loss of ambulation. The median age at loss of ambulation will be reported by corticosteroids use at baseline. The Kaplan-Meier curves will also be displayed. The age at loss of ambulation is defined as age of the disease progression reported as the adverse event or age at the time to run/walk 10 meters > 30 seconds, whichever occurs earlier. The subjects who are ambulatory at the end of study or discontinuation will be censored on the last valid timed function tests assessment date. Age on that date will be used in the analysis. A sensitivity analysis will be performing based on the loss of ambulation defined only by disease progression AE.

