In Study 019, the loss of ambulation is defined as the disease progression reported as the adverse event or the time to run/walk 10 meters > 30 seconds, whichever occurs earlier. The event age is the one on the AE start date. The subjects who are ambulatory at the end of study will be censored on the last valid timed function tests assessment date. Age on that date will be used in the analysis. In the CINRG data, the age at the earliest report of the non-ambulation or the time to run/walk 10 meters > 30 seconds, whichever earlier, will be picked as the event age. If subjects in CINRG data do not report non-ambulation, the age at the last report of ambulation will be chosen as the censor age. A sensitivity analysis will be performing based on the loss of ambulation defined only by disease progression AE.

Similarly, the age at FVC < 1 liter is the one at the first time FVC < 1 liter. If subjects do not have FVC < 1 liter, the age at the last non-missing FVC assessment will be chosen as the censor age.

For CINRG data only, the observed values will be summarized descriptively for each actual age on 6MWT, time to run/walk 10 meters, time to stand from supine, NSAA total and linear scores, %-predicted FVC, %-predicted FEV1, PEF and EK total scores by corticosteroid use at baseline (yes or no) and overall based on the matched populations.

NSAA score derivation algorithms in Study 019 will be applied to CINRG data.

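### An adverse-event onset with the month missing is dated January 1 (or the first dose) and can then serve as the age at loss of ambulation, even ahead of a 10-meter test the boy passed

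*SAP*

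**What the plan says.** **The event.** SAP 5.8.2 states: "The age at loss of ambulation is defined as age of the disease progression reported as the adverse event", or the age when the 10-meter run/walk exceeds 30 s, taking the earlier of the two. SAP 8.2.1 repeats this for the CINRG comparison and adds: "The event age is the one on the AE start date". Only 8.2.1 names the start date.

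**The date rule.** SAP 6.4.1 opens: "The following imputation rules only apply to cases in which the start date is incomplete (ie, partially missing) for adverse events". It then sets:

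- Day and month missing, year after the first-dose year: "If the year is after the year of the date of the first dose double-blind study drug, then January 1 will be assigned".
- Day and month missing, same year as the first dose: "then the day and month of the date of the first dose of double-blind study drug will be assigned to the missing fields".
- Month missing, day known: "The day will be treated as missing and both month and day will be replaced according to the above procedure".
- Day missing, month after the first-dose month: "then the first day of the month will be assigned to the missing day".

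The only check is against a complete stop date: if the imputed start falls after it, the stop date is used.

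**Censoring and use.** In both sections, boys still walking are censored at their last valid timed function test. The Kaplan-Meier analyses of this age are in 5.8.2, 5.9.2 and 5.9.3, and 8.2.1 adds a log-rank test against CINRG. The one planned sensitivity analysis uses the disease-progression event alone.

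**The concern.** Choosing an early date is a normal convention for deciding whether an adverse event is treatment-emergent (SAP 5.7.1), where an error of months rarely changes the answer. Here nothing confines the rule to that purpose, and the same date can become the event time of an efficacy analysis.

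Three features make the error hard to catch. The earlier of two dates is taken, so a later failed test cannot correct an adverse-event date that is too early. The stop-date check can only move a start date earlier. The sensitivity analysis drops the walking test and keeps the imputed date.

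The result can also contradict the SAP's own evidence. Censoring at the last valid timed function test treats that test as proof of walking, yet an imputed event can be placed before such a test. At stake are the Study 019 median age at loss of ambulation, its subgroup curves, and the log-rank comparison with CINRG.

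**Working it through.** The documents give no figure on this point, so there is none to reproduce. The anchor is read as the first Study 019 dose, although 6.4.1 calls it double-blind drug and this study is open-label.

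**Inputs.** The rules are those of SAP 6.4.1. 10-meter tests are every 48 weeks, or 336 days (Protocol 7.2.17), with a window of ±7 days (Protocol Table 4). Treatment lasts 240 weeks, or 1680 days. Assumptions: first-dose dates of Jan 1, Jan 15, Apr 1, Jul 1 and Oct 1, 2013; true onset equally likely on each of days 1 to 1680; a boy tested before his true onset passes the test.

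**Size of the error** (true date minus imputed date):

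| What is missing | Imputed to | Largest error | Mean error |
|---|---|---|---|
| Month, later year | January 1 | 364 days (365 in a leap year) | 170-178 days |
| Month, first-dose year | First dose | 364 / 350 / 274 / 183 / 91 days for the five first-dose dates | 183 / 176 / 138 / 92 / 46 days |
| Day only | First of the month (first dose, in the first-dose month) | 30 days | about 15 days |

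**Is there a test to contradict?** Tests are at most 336 + 14 = 350 days apart, so every full calendar year on study contains a scheduled one.

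**How often does a test fall between the imputed and the true date?** For month-missing onsets in later years, the shares for the five first-dose dates are 20%, 16%, 71%, 68% and 41%. Averaged over all positions of the test schedule in the year, with onset uniform over 365 days:

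(∫₀³³⁶ d/336 dd + (365 − 336)) / 365 = (168 + 29) / 365 = 0.54.

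In the first-dose year, a scheduled post-baseline test can follow the imputed date only if day 336 after the first dose falls in that year, that is, with a first dose in about the first four weeks of January.

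**Example.** First dose 1 Jul 2013. Week 96 test on 4 May 2015 (672 days later), passed. True onset 20 Nov 2015, recorded only as 2015. Imputed date 1 Jan 2015: 323 days early (323/365.25 = 0.88 year), and 123 days before the passed test.

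**Effect on mean event age.** Shift = share of events with the month missing × 176.1/365.25 (mean error for a first dose on Apr 1). The shares are assumed.

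| Share | Shift (years) |
|---|---|
| 2% | 0.01 |
| 5% | 0.02 |
| 10% | 0.05 |
| 20% | 0.10 |

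**Alternatives** (first dose Apr 1, later years): as written, 0 to 365 days early, mean 176. With only a floor on the day after the last passed test, 0 to 335 days early, mean 148, with no contradiction. With only a mid-year date (July 2), error within about ±183 days, mean about −6 (slightly late), but contradictions remain possible. A floor and a midpoint are both needed.

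**The case against.** The strongest objection is that this will seldom matter. Protocol 8.3 requires an onset date for each adverse event, and Protocol 7.2.24 has events assessed at every clinic visit, 12 weeks apart, so an unknown month for loss of walking should be uncommon. The possible shift is also small beside the spacing of the tests: a loss found only by test would be dated on average 336/2 = 168 days late (0.46 year) if onset is uniform between tests. And the direction is conservative: Study 019 events come out too early, so the rule cannot create an apparent benefit over CINRG. All of this stands. It limits the size of the point, but it does not defend a stated rule that can date an event before a passed test.

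A reader might also infer more than the documents support:

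- **That any partial date can move by up to a year.** That needs a missing month.
- **That an event dated to the first dose contradicts the Screening test.** Screening comes first. Such a date is implausible for a boy who entered as ambulatory, but it is not contradictory.
- **That this is the study's main time-to-event result.** The primary endpoint is safety, and age at loss of ambulation is not among the endpoints in Protocol 3.3 or SAP 3.3.
- **That CINRG dates are free of back-dating.** SAP 8.2.1 uses the earliest report of non-ambulation or the first failed test there, and does not say how partial dates were handled.
- **That 54% of month-missing dates will contradict a passed test.** It is an average over test timing; by first-dose date the share runs from about 16% to 71%.

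**Conclusion.** The point holds on the text. In SAP 8.2.1 the age at loss of ambulation comes from an adverse-event start date that 6.4.1 may have imputed, with no exception and no check against walking data. For 5.8.2 this is an inference: it does not name the start date, but no other date rule is given.

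The material error is confined to onsets with the month missing. In later years it reaches 364-365 days, with a mean of about six months under uniform onset, and the imputed date can precede a passed test. In the first-dose year the event goes to the first dose. The effect on the mean, about 0.01-0.10 year, rests on an assumed share of 2-20% of events; the true share is not given and is probably low. The bias is against ataluren. This is a modest but real defect in how an event is dated, and correcting the double-blind wording would not remove it.

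**What to change.** State in SAP 5.8.2 and 8.2.1 that the 6.4.1 imputed date is not used for age at loss of ambulation. For a partial onset of a disease-progression event, use the midpoint of the recorded period, with these bounds:

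- **Below:** the later of the first Study 019 dose and the last valid 10-meter test of 30 s or less.
- **Above:** the earlier of the first 10-meter test over 30 s and the event's stop date.

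Apply the bounds to recorded times, before 5.8.2 resets values over 30 s to 30 s. If the bounds conflict with the recorded period, query the date. In the example, the period runs from 4 May (day 124) to 31 Dec 2015 (day 365), assuming no earlier stop date; the next test, 336 days after 4 May, falls in 2016. The midpoint is day (124 + 365)/2 = 244.5. True onset is day 324, so the error falls from 323 days to about 80, and the passed test is respected.

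Keep the 6.4.1 date as a sensitivity analysis, report how many events had a missing month, and apply the same rule to any partial CINRG dates.

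The cost is one sentence and one extra derivation. Study 019 event ages become slightly later, a shift in the drug's favor, which the sensitivity analysis makes visible.
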